1.1.1. Treatment Options

Multiple combinations of the new agents are being explored in ongoing studies. Minimal randomized data are yet available regarding relative efficacy of such combinations. The optimal strategy in managing progressive RCC after resistance to initial therapy is in rapid evolution. Recent trials of the PD1 inhibitor Nivolumab and the VEGFR/MET TKI Cabozantinib in the previously treated setting showed efficacy benefit for these agents when compared to everolimus; however, as of this writing, neither of these newer agents have been FDA-approved for metastatic RCC. Since the availability of multiple agents, switching drugs in the face of progression has instead become a standard practice.

Checkpoint inhibitor therapy is also particularly active in RCC, particularly with PD1 inhibitors. A recent paper by Motzer et al (JCO 2014) reported the results of a randomized phase II trial testing the BMS PD1 inhibitor Nivolumab in mRCC. A total of 168 patients were randomly assigned to three dose levels of nivolumab 0.3- (n = 60), 2- (n = 54), and 10-mg/kg (n = 54). Median PFS was 2.7, 4.0, and 4.2 months, respectively (P = .9). Respective ORRs were 20%, 22%, and 20%. Median OS was 18.2 months (80% CI, 16.2 to 24.0 months), 25.5 months (80% CI, 19.8 to 28.8 months), and 24.7 months (80% CI, 15.3 to 26.0 months), respectively. Nivolumab was also recently reported to improve OS compared to everolimus in a large randomized phase III trial.

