8.3. Follow-up Phase

Once a subject has completed the End-of-Treatment Visit they will enter the Follow-up Phase. Once subjects experience TF, relapse, or start use of alternative anticancer therapy (for subjects who have not withdrawn consent), they will be contacted approximately every 3 months (± 14 days) by clinic visit or telephone until death, subject withdrawal, lost to follow-up, study termination by the study sponsor, or up to 6 months whichever occurs first.

- Survival status, including other malignancies
- Subsequent anticancer therapy

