9.2. Withdrawal from Study Treatment

Study treatment will be discontinued in the event of any of the following events:

1. Unacceptable toxicity
2. Treatment failure or no evidence of clinical benefit per investigator assessment
3. An intercurrent illness or adverse event that prevents further ibrutinib administration.

4. Withdrawal of consent for treatment by subject
5. Investigator decision (such as chronic noncompliance, significant protocol deviation, or best interest of the subject)
6. Study termination by Pharmacyclics or study sponsor
7. Subject becomes pregnant
8. Nivolumab is held for greater than 42 days (the subject can stay on study with Ibrutinib only)
9. Ibrutinib is held for greater than 4 weeks. If Ibrutinib therapy is held for greater than 4 weeks, then the subject must discontinue from the nivolumab as well

All subjects, regardless of reason for discontinuation of study treatment will undergo an End of Treatment Visit and be followed for treatment failure and survival.

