10.2.2. Secondary Endpoints

Secondary analytic objectives are to provide preliminary assessments of the RECIST Response Rate, Overall Survival, and Safety of this treatment combination.

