10.5. Statistical Methods

Primary endpoint: Progression-free survival (PFS) as the number of months from baseline to death or progression, defined in Appendix 4. The duration of PFS will be summarized descriptively using Kaplan-Meier survival plots and life tables. The number and proportion with PFS of 6 months or more will be reported, adjusting for censoring using the life-table approach. If the number with PFS at least six months is 15 or more out of 25 evaluable patients, this will constitute evidence supporting an improvement over historic PFS rates.

Secondary endpoints: RECIST response will be calculated as in Appendix 4, and will be summarized by the number and percentage of patients, accompanied by 2-sided exact 95% confidence intervals. Overall survival will be summarized descriptively by Kaplan-Meier curves and life table estimates, as for PFS. Number and type of adverse events will be summarized descriptively by system organ class affected and by grade of event, overall and by dose. Vital signs and laboratory test results will be summarized descriptively (mean, SD, range) overall and by dose.

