14. APPENDICES

Appendix 1. Schedule of Assessments

Study Visits	Screening Phase	Treatment Phase (1 cycle = 28 days)							Suspected PD	End-of-Treatment ^a	FU ^b
		Cycle 1		Cycle 2		Cycles 3–7		Cycles 8 and beyond			
		D1 (baseline)	D15	D1	D15	D1	D15	D1			
Study Visit Windows	-28 days			± 3 days					Any time	30 days after treatment d/c	q 3 mos
Informed consent	X										
Confirm eligibility	X	X									
Medical history	X										
Review concomitant medications	X	X	X	X	X	X	X	X		X	
Review adverse events ^c			X	X	X	X	X	X		X	
Study drug compliance review ^d			X	X	X	X		X			
Height	X										
Physical exam, vital signs, weight, ECOG	X	X	X	X	X	X		X	X	X	X
Disease assessment [†] :											
CT/MRI scan	X					X		X	X		X
Overall response assessment						X		X	X		X
Hematology	X	X	X	X	X	X	X	X	X	X	
Serum chemistry [*]	X	X	X	X		X		X	X	X	
TSH ^f	X	X				X		X		X	
Creatinine clearance (Cockcroft-Gault)	X									X	
PT/INR and PTT	X										
Hepatitis serologies	X										
Pregnancy test	X	X									
12 lead ECG	X	As clinically indicated [‡]									
Urine test	X										
Archival Specimen	X										
Blood for Translational Studies ^e	X		X							X	
Urine for Translational Studies	X		X							X	
Any new anticancer therapy											X
Study Drug Administration											
Nivolumab infusion		Every 2 weeks									
Ibrutinib (continuous)		X	X	X	X	X	X	X			

Abbreviations: D = day; d/c = discontinuation; PD = progressive disease; FU = follow-up, TSH = thyroid stimulating hormone.

Nivolumab: 240 mg IV every 2 weeks

[†]Disease assessment to be performed every 8 weeks

*Laboratory testing prior to Nivolumab treatment (will be done before every 2 doses of Nivolumab treatment, every 4 weeks).

[‡]ECG's may be performed at the investigator's discretion, particularly in subjects with arrhythmic symptoms (eg, palpitations, lightheadedness) or new onset dyspnea

a. An EOT visit will occur 30 ± 7 days from the last dose of study drug or prior to the start of a new anticancer treatment.

b. Once subjects experience TF, relapse, or start use of alternative anticancer therapy (for subjects who have not withdrawn consent), they will be contacted approximately every 3 months (±14 days) by clinic visit or telephone until death, subject withdrawal, lost to follow-up, study termination by the study sponsor, or up to 6 months whichever occurs first.

c. AEs are reported from the time the patient signs the Informed Consent Form until 30 days following last dose of study drug.

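### Survival contact stops at six months with no stated starting point, which would leave overall survival with avoidably few deaths

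*Combined protocol and SAP*

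**What the plan says.** Section 8.3 opens 3-monthly contact, by clinic visit or telephone, with a trigger: "Once subjects experience TF, relapse, or start use of alternative anticancer therapy". Contact ends at death, withdrawal, loss to follow-up, "study termination by the study sponsor, or up to 6 months whichever occurs first". Appendix 1 footnote b repeats this. The start of the six months is not written in either place. Treatment failure, one of the three triggers, appears in the abbreviations list but is not defined.

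OS is a named endpoint in section 10.2.2: "Secondary analytic objectives are to provide preliminary assessments of the RECIST Response Rate, Overall Survival, and Safety of this treatment combination". Section 10.5 gives the analysis: "Overall survival will be summarized descriptively by Kaplan-Meier curves and life table estimates, as for PFS". There is no OS event target, hypothesis or censoring rule.

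Other sections point to survival follow-up without the limit:
- Section 3.2 says that survival status will be recorded.
- Section 9.2 says that all subjects who stop treatment will "be followed for treatment failure and survival".
- Section 9.3 lists the reasons for leaving all follow-up, and six months elapsed is not among them.
- Section 11.4.4 mentions follow-up for OS after progression.
- Section 12.7 sets a deadline for a form when a death becomes known after a patient is off study.

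None of these sets a contact schedule beyond six months. The synopsis gives a study duration of 30 months.

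**The concern.** A limit of six months from the trigger gives about two contacts at a 3-month interval. The protocol's own background suggests that most deaths come later than that. For single-agent nivolumab at three doses, section 1.1.1 reports "Median PFS was 2.7, 4.0, and 4.2 months, respectively", and then "Median OS was 18.2 months (80% CI, 16.2 to 24.0 months), 25.5 months" and 24.7 months.

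Two things are at stake. First, deaths that occur during the study but after the last scheduled contact may never reach the OS analysis. Second, follow-up ends at a time fixed by the patient's disease course, through progression, treatment failure or new therapy. Ordinary Kaplan-Meier estimation assumes that censoring is unrelated to prognosis.

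**Working it through.** **1. The plan's own figure.** With n = 25 and success at 15 or more, the exact binomial gives P(X ≥ 15 | 0.40) = 0.0344 and P(X ≥ 15 | 0.70) = 0.902. This agrees with the one-sided 0.034 and 90% in section 10.3. The limit does not touch this rule: a window that closes six months after a trigger cannot close before month 6 from baseline. The documents give no corresponding figure for OS.

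**2. Scale from section 1.1.1.** Median OS minus median progression-free survival (PFS) is 18.2 − 2.7 = 15.5, 25.5 − 4.0 = 21.5 and 24.7 − 4.2 = 20.5 months. A difference of medians is not a median of differences, so this serves for scale only. All three are well above six months.

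**3. Base model.**
- From the documents: 30 patients; 30-month study; 6-month PFS of 40%, the null rate in section 10.3.
- Assumed: exponential times; 10% of PFS events are deaths; median survival after progression 14 months; uniform accrual over 18 months; clock starts at progression; no deaths captured after the limit.
- PFS event rate: −ln(0.4)/6 = 0.1527 per month (median 4.5 months). The implied median OS is 19.1 months, inside the 18.2 to 25.5 range of section 1.1.1.
- Chance that a patient who progresses dies within the window: 1 − 2^(−6/14) = 0.257.

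| Per 30 patients, base case | Six-month limit | Common cut-off |
|---|---|---|
| Deaths observed | 9.2 | 15.9 |
| At risk at 12 months | 10.3 | 20.4 |
| At risk at 18 months | 2.7 | 10.5 |
| Median OS reached (4,000 simulated trials) | 48% | 90% |
| SD of 18-month estimate (points) | 14.3 | 9.8 |

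Share of deaths lost: 1 − 9.2/15.9 = 42%.

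**4. Varying the assumptions**, one change from base unless stated:

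| Scenario | Deaths, limit vs cut-off | Lost | Bias at 18 months (points) |
|---|---|---|---|
| Base | 9.2 vs 15.9 | 42% | about +5 |
| Post-progression median 21, no deaths before progression | 4.9 vs 11.0 | 55% | +6.0 |
| Weibull shape 1.3 after progression | 7.9 vs 16.2 | 51% | +9.3 |
| Weibull shape 0.6 | 11.3 vs 15.7 | 28% | −1.8 |
| Death share 32.4% | 13.9 vs 19.0 | 27% | 0 |
| Death share 40% | 15.6 vs 20.1 | 22% | −1.2 |
| Limit at progression + 7 months | 10.0 vs 15.9 | 37% | +3.6 |
| 6-month PFS 70% | 6.5 vs 10.5 | 38% | +5.7 |
| 6-month PFS 70%, death share 40% | 11.3 vs 14.0 | 19% | +2.4 |
| Same, 24-month accrual | 10.1 vs 12.1 | 17% | +2.3 |

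This family spans 17% to 55% lost. With 6-month PFS of 70% and other inputs at base, the number at risk at 18 months falls from 14.1 to 9.1.

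**5. A second family**, with survival after progression tuned so that median OS is 18.2 or 25.5 months. With all deaths following progression, 24% to 63% are lost. With 10% of patients dying without progression and PFS and post-progression survival correlated to varying degrees, 12% to 48% are lost. Starting the clock at the End-of-Treatment visit gives 26% to 58%.

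**6. Direction of the bias.** Patients censored by the limit have progressed, and those who remain at risk longest have not. The estimate reads high if the death hazard is higher after progression than before. In the base case the hazards are ln 2/14 = 0.0495 per month after and 0.10 × 0.1527 = 0.0153 before, giving a bias of about +2 points at 12 months (sampling SD 9.5) and +5 at 18. At a 32.4% death share the two hazards are equal (0.324 × 0.1527 = 0.0495) and the bias is zero. Beyond that share it turns negative, as it does when the hazard falls steeply after progression. The range in the first family is −0.7 to +3.2 points at 12 months and −1.9 to +9.3 at 18.

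**The case against.** The strongest reply is that the documents never say deaths after the limit are discarded. Sections 3.2, 9.2, 9.3, 11.4.4 and 12.7 can be read as open-ended intent to learn of deaths, and a form exists for deaths off study. This stands in part: zero capture after six months is an assumption of the working, not a statement in the protocol. But reporting a death when it happens to become known is passive, and no section schedules the contact that would reveal it.

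The clock start is also assumed. Section 8.3 first describes entry to follow-up after the End-of-Treatment visit, and new therapy or treatment failure can start the clock as well as progression. So censoring is linked to disease course, not to progression alone. Under the End-of-Treatment reading the loss is of similar size.

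A reader might take the 42% as what the trial will lose. The documents do not fix it. Accrual, survival after progression and the share of deaths without progression are all missing. The section 1.1.1 figures come from single-agent nivolumab, while section 4.1 admits any histology, any number of prior lines, prior nivolumab and ECOG 2.

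Finally, OS here is preliminary and descriptive in 30 patients, and short follow-up may be a resource choice. That limits the severity. It does not explain an undefined limit that sits beside open-ended wording elsewhere.

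**Conclusion.** The point holds as a cheap improvement of modest severity. The limit is in the current text twice, its start is undefined, and no section schedules contact beyond it. Read from the trigger, and without passive capture, it costs OS a substantial share of the deaths inside the 30-month study: 17% to 55% in the first family of scenarios and 12% to 63% across all models. It also thins the curve at 18 months, severely at 6-month PFS of 40% and less so at 70%.

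Two stronger inferences are not supported. One is that OS will be overstated: upward bias of a few points is common in the scenarios, but zero and negative values arise under assumptions that the documents do not exclude. The other is that the trial's conclusion is at risk: the 15-of-25 rule is unaffected and no decision rests on OS. The loss of information, unlike the bias, had the same direction in every scenario run.

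**What to change.** In section 8.3 and Appendix 1 footnote b, delete the six-month limit. Contact all patients for survival every 3 months until death, withdrawal, loss to follow-up or one common study-end cut-off. In section 10.5, state that OS is censored at the date last known alive.

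The cost is additional telephone contacts for at most 30 patients, and a protocol amendment, which under section 12.9 needs the ibrutinib supplier's review and approval and then IRB approval. The gain is bounded: in the base case about 10 of 30 are at risk at 18 months and about 4 at 24 even after the change, so it yields a usable curve to about 18 months rather than a long-term estimate.

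If the limit is kept, define when its clock starts, report numbers at risk beside the curve, and confine OS reporting to about 12 months. That contains the bias but does not recover the lost deaths.

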9. SUBJECT COMPLETION AND WITHDRAWAL

9.1. Completion

A subject will be considered to have completed the study if he or she has died before the end of the study, has not been lost to follow up, or has withdrawn consent before the end of study.

9.2. Withdrawal from Study Treatment

Study treatment will be discontinued in the event of any of the following events:

1. Unacceptable toxicity
2. Treatment failure or no evidence of clinical benefit per investigator assessment
3. An intercurrent illness or adverse event that prevents further ibrutinib administration.

4. Withdrawal of consent for treatment by subject
5. Investigator decision (such as chronic noncompliance, significant protocol deviation, or best interest of the subject)
6. Study termination by Pharmacyclics or study sponsor
7. Subject becomes pregnant
8. Nivolumab is held for greater than 42 days (the subject can stay on study with Ibrutinib only)
9. Ibrutinib is held for greater than 4 weeks. If Ibrutinib therapy is held for greater than 4 weeks, then the subject must discontinue from the nivolumab as well

All subjects, regardless of reason for discontinuation of study treatment will undergo an End of Treatment Visit and be followed for treatment failure and survival.

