3.1.1. Study Schema

*DLT assessment after 1 cycle (4 weeks)

*DLT = Grade III or higher SAE attributed to treatment

**Patients will have two de-escalation dose levels for (-1 and -2) for all patients based on interim toxicities.

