3.2.1. Study Population And Treatment

The study will enroll adult subjects with pathologically determined renal cell cancer. This study will be conducted at the University of California Davis Comprehensive Cancer Center and at another site that is yet to be determined. There will be a total of 2 US sites.

Ibrutinib in combination with nivolumab will be investigated. The assigned treatment (Ibrutinib in combination with nivolumab) will continue in subjects for a maximum of 1 year or until progression, unacceptable or intolerable toxicity, physician choice (if in best interest of patient), or patient withdrawal for any reason. In the event that the patient is unable (due to toxicity or tolerability issues) or unwilling to receive both agents concurrently after the first two cycles, then single agent nivolumab can be administered at the investigator's discretion to complete one year of therapy. Treatment with ibrutinib will continue until either disease progression OR physician/patient choice OR unacceptable or intolerable toxicities.

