3.2.2. Dose Selection

The selected dose of ibrutinib ranges from 420-560 mg (2-4 x 140 mg capsules) once daily. Although ibrutinib is rapidly eliminated from the plasma after oral administration, once daily dosing with ibrutinib is adequate to sustain maximal pharmacodynamic activity for 24 hours postdose at dose levels \geq 2.5 mg/kg. A dose greater than 2.5 mg/kg was considered necessary to achieve consistent, full BTK occupancy, in previous PCYC studies. In Study PCYC-04753, the BTK occupancies for the 2.5 mg/kg/day to 12.5 mg/kg/day cohorts and for the 560 mg continuous dosing cohort, were all above 90% at either 4 or 24 hours after drug administration.

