7. STUDY EVALUATIONS

7.1. Description of Procedures

A cycle has a duration of 28 days throughout this study.

All screening clinical and laboratory assessments must be performed within 28 days of Study Day 1 and prior to the first dose of study treatment.

All study tests and procedures should be evaluated at the study center at which the subject was enrolled.

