8.2. Treatment Phase

Treatment with ibrutinib in combination with nivolumab will continue for a maximum of one year or until 1) tumor progression; 2) unacceptable or intolerable toxicity; 3) patient withdrawal for any reason; 4) physician choice if in the best interest of the patient. Treatment with Ibrutinib will continue until either disease progression, or physician choice, or patient choice, or unacceptable or intolerable toxicities. Investigator discretion as to continuing single agent nivolumab for a maximum of one year will be allowed for patients who are unable to receive the doublet due to toxicity or patient preference.

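### Section 9.2 makes nivolumab stop once ibrutinib has been held for more than 4 weeks, while 3.2.1 and 8.2 let a patient who cannot take both drugs because of toxicity continue nivolumab alone to one year

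*Combined protocol and SAP*

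**What the plan says.** Three sections govern what happens to nivolumab when ibrutinib cannot be given.

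- **9.2, item 9.** Study treatment is discontinued if ibrutinib is held for more than 4 weeks, and the item adds: "If Ibrutinib therapy is held for greater than 4 weeks, then the subject must discontinue from the nivolumab as well". It gives no exception, no cycle limit and no role for investigator judgement.
- **3.2.1.** The permission covers a patient who, because of toxicity or tolerability, cannot take the two drugs together, or is "unwilling to receive both agents concurrently after the first two cycles, then single agent nivolumab can be administered" at the investigator's discretion, up to one year of therapy.
- **8.2.** "Investigator discretion as to continuing single agent nivolumab for a maximum of one year will be allowed for patients who are unable" to take the doublet because of toxicity or patient preference. There is no two-cycle condition.

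Two other items in the 9.2 list bear on the reading. Item 3 is "An intercurrent illness or adverse event that prevents further ibrutinib administration". Item 8 covers the reverse case, "Nivolumab is held for greater than 42 days (the subject can stay on study with Ibrutinib only"), so the list does state a single-agent exception, but only for ibrutinib.

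Section 7.1 fixes the timing: "A cycle has a duration of 28 days throughout this study".

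Separately, 3.2.2 reads: "The selected dose of ibrutinib ranges from 420-560 mg (2-4 x 140 mg capsules) once daily".

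**The concern.** A toxicity that keeps a patient off ibrutinib for more than 4 weeks is a foreseeable event. Table 1 in 5.3.1.4 withholds ibrutinib until recovery, and 5.3.1.5 holds it in severe hepatic impairment until improvement. Neither sets a maximum length. Such a patient must stop nivolumab under 9.2 item 9, and may continue it for up to a year under 8.2 and, after two cycles, under 3.2.1.

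The trial has two sites and a single-arm primary endpoint, PFS at 6 months. One site could take the patient off both drugs and the other could keep the patient on nivolumab, and each could point to the protocol. The treatment strategy that the 6-month result describes would then depend on which section a site happened to apply.

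**Working it through.** The plan gives no figure for this point, so the check is a comparison of rules plus day counting.

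**Inputs**

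- Cycle length: 28 days (7.1). Two cycles end on day 2 × 28 = 56, and cycle 3 starts on day 57.
- Limit in 9.2 item 9: a hold longer than 4 weeks, that is, longer than 28 days.
- First ibrutinib dose: taken in clinic on Day 1 (5.3.1.2, 8.2.1). The first missed day is therefore day 2 at the earliest.

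**When the limit is passed**

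If the first missed day is *d*, the 29th missed day is *d* + 28.

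| First missed day | Limit passed on | 9.2 item 9 | 3.2.1 | 8.2 |
|---|---|---|---|---|
| 2 (earliest) | 2 + 28 = 30 | nivolumab stops | not yet available | nivolumab alone allowed |
| 28 (last day of cycle 1) | 28 + 28 = 56 | nivolumab stops | not yet available | nivolumab alone allowed |
| 29 (first day of cycle 2) | 29 + 28 = 57 | nivolumab stops | nivolumab alone allowed | nivolumab alone allowed |
| later than 29 | later than 57 | nivolumab stops | nivolumab alone allowed | nivolumab alone allowed |

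The table is for a hold caused by toxicity. It gives two regimes:

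1. Hold starting in cycle 1 (limit passed on days 30 to 56): item 9 conflicts with 8.2. Section 3.2.1 does not yet apply, so 3.2.1 and 8.2 also differ from each other.
2. Hold starting on day 29 or later: item 9 conflicts with both 3.2.1 and 8.2.

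**Does it fall inside the primary endpoint window?** The plan does not give 6 months in days. Six cycles are 6 × 28 = 168 days, which is less than six calendar months. A hold starting on any day from 2 to 168 − 28 = 140 passes the limit by day 168, so both regimes can occur within the window.

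**Is there a tie-break?** Sections 3.2.1, 8.2 and 9.2 do not refer to each other on this point, and nothing ranks them.

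**Capsule count in 3.2.2.** 2 × 140 = 280 mg, 3 × 140 = 420 mg and 4 × 140 = 560 mg. Two to four capsules are 280 to 560 mg, which does not match the stated 420 to 560 mg.

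**The case against.** **A hold is not a permanent stop.** Item 9 speaks of ibrutinib being held, and Table 1 in 5.3.1.4 does separate withholding (first to third occurrence) from discontinuing (fourth). A patient who permanently stops ibrutinib after two cycles could come under 3.2.1 without ever having a hold of more than 4 weeks. This narrows the overlap but does not remove it: a toxicity hold that runs past 4 weeks still meets item 9 and the permission in 8.2.

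**Item 3.** A reader might infer that item 3 independently forces nivolumab to stop. The text does not settle this. Item 8 stands under the same lead-in about discontinuing study treatment and yet leaves the patient on ibrutinib, so the lead-in need not mean both drugs. Item 9 also has to name nivolumab expressly. Item 3 can be read as stopping ibrutinib only; it is ambiguous and may add to the conflict. The explicit conflict is item 9.

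**Every long hold.** A reader might also infer that any ibrutinib hold beyond 4 weeks creates the contradiction. It does not. Holds for surgery (6.4) or therapeutic anticoagulation (6.2.4) can trigger item 9 without clearly meeting the toxicity, tolerability or preference conditions of 3.2.1 and 8.2.

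**Effect on the result.** PFS runs from baseline to progression or death whatever treatment is given (10.5), and 9.2 keeps patients who stop treatment in follow-up. The single-agent option is discretionary, so if the sponsor retains it, treatment will still vary after reconciliation. Both points stand. That variation would then be permitted by one rule instead of arising from opposing ones.

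**Dose levels.** The schema footnote, "Patients will have two de-escalation dose levels for (-1 and -2) for all patients based on interim toxicities", against a table in 5.2.1 that lists only levels 0 and −1, might suggest a missing dose level. The schema itself is not available to read, Table 1 gives its steps in mg, and the lower start in 5.3.1.5 is a stated subgroup rule. Only the capsule count in 3.2.2 remains.

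**Analysis set.** The reference in 10.3 to all enrolled patients might suggest a second primary population. That sentence explains itself as pooling over dose levels, and 10.4.2 names the evaluable population as primary. The lack of a cut-off when the number analysed is not 25 is a separate matter.

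**Conclusion.** The contradiction is in the current text and holds for a defined group: patients whose ibrutinib is held for toxicity for more than 4 weeks. For holds starting on day 29 or later, 9.2 item 9 opposes both 3.2.1 and 8.2; for holds starting in cycle 1, it opposes 8.2 only.

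This rests on reading 4 weeks as 28 days, on a first dose on Day 1, and on taking the 3.2.1 permission to begin once cycle 2 is complete. Confidence is high for item 9 and limited for item 3.

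A reader might infer that the 6-month PFS result would be biased. The documents do not support that: they do not say how many patients would be affected or what continuing nivolumab would do to PFS. What is established is that the treatment rule is not fixed. It should be corrected, because it determines what patients receive and the correction is cheap. The 3.2.2 mismatch is a minor wording slip.

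**What to change.** Reconcile 9.2 items 3 and 9 with 3.2.1 and 8.2 so that one rule applies. The revised text should settle:

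- whether nivolumab may continue alone after an ibrutinib hold of more than 4 weeks, and for which reasons for the hold;
- whether the two-cycle condition in 3.2.1 applies, since 8.2 omits it;
- whether a prolonged hold and permanent discontinuation of ibrutinib are treated alike;
- whether item 3 refers to ibrutinib only or to both drugs.

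Which rule to adopt is for the sponsor. In 3.2.2, the sponsor should also reconcile the capsule count with the dose range.

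The cost is amendment wording only, with no additional patients or procedures. The sample size and success criterion are not affected.

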6.2.4. Antiplatelet Agents and Anticoagulants

Warfarin or vitamin K antagonists should not be administered concomitantly with ibrutinib. In an in vitro platelet function study, inhibitory effects of ibrutinib on collagen-induced platelet aggregation were observed. Supplements such as fish oil and vitamin E preparations should be avoided. Use ibrutinib with caution in subjects requiring other anticoagulants or medications that inhibit platelet function. Bleeding events of any grade, including bruising and petechiae, occurred in subjects treated with ibrutinib. Subjects with congenital bleeding diathesis have not been studied. For guidance on ibrutinib and the use of anticoagulants during procedures/surgeries see Section 6.4.

Subjects requiring the initiation of therapeutic anticoagulation therapy (eg, atrial fibrillation), consider the risks and benefits of continuing ibrutinib treatment. If therapeutic anticoagulation is clinically indicated, treatment with ibrutinib should be held and not be restarted until the subject is clinically stable and has no signs of bleeding. Subjects should be observed closely for signs and symptoms of bleeding. No dose reduction is required when study drug is restarted.

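### The nivolumab stopping rules in Section 9.2 (items 9 and 3) conflict with the single-agent nivolumab option in Sections 3.2.1 and 8.2

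*Combined protocol and SAP*

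**What the plan says.** The permissive text is in two places. Section 3.2.1 covers a patient whom toxicity or poor tolerability keeps from the combination, and equally one who is "unwilling to receive both agents concurrently after the first two cycles, then single agent nivolumab can be administered". The choice lies with the investigator, and nivolumab alone may run until one year is reached. Section 8.2 repeats it: "Investigator discretion as to continuing single agent nivolumab for a maximum of one year will be allowed for patients who are unable to receive" both drugs together, the reasons given being toxicity or patient preference. Section 8.2 does not carry the two-cycle condition.

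The restrictive text is the list in Section 9.2 of events that end study treatment.

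- Item 9: "If Ibrutinib therapy is held for greater than 4 weeks, then the subject must discontinue from the nivolumab as well". No exception is stated.
- Item 3: an illness or adverse event that prevents further ibrutinib ends study treatment.
- Item 1: unacceptable toxicity does the same, without saying which drug must be the cause.
- Item 8 treats the mirror case differently. When nivolumab has been held for more than 42 days, the subject may remain on ibrutinib alone.

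**The concern.** The same patient falls under both sets of rules. Someone who stops ibrutinib for toxicity after two cycles qualifies for nivolumab alone under 3.2.1 and 8.2. Four weeks later that patient must stop nivolumab under item 9, and on a literal reading of item 3 must stop at once. The list shows that its authors knew how to write a single-agent exception, because item 8 has one and item 9 does not.

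At stake is the loss of nivolumab for a patient whose only difficulty is with ibrutinib, although two sections expressly allow it. The conflict also lets identical patients be treated differently at the two planned sites. Nivolumab exposure before the 6-month primary time point would then depend on which section a site follows.

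**Working it through.** **1. The plan's own design figures (Section 10.3).** With X binomial, n = 25 and success at 15 or more, P(X ≥ 15 | 0.40) = 0.0344 and P(X ≥ 15 | 0.70) = 0.9022. The stated one-sided level of 0.034 and 90% power reproduce. The conflict does not enter this calculation.

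**2. The rules side by side.**

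| Situation | 3.2.1 and 8.2 | 9.2 |
|---|---|---|
| Ibrutinib held more than 4 weeks for toxicity | Nivolumab alone allowed, to one year | Item 9: nivolumab must stop |
| Adverse event prevents any further ibrutinib | Nivolumab alone allowed, to one year | Item 3: study treatment ends |
| Nivolumab held more than 42 days | Not addressed | Item 8: ibrutinib alone allowed |

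The first two rows conflict.

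**3. Doses at stake.** Inputs: nivolumab every 2 weeks (5.3.2.2) for up to one year (5.3.4), 28-day cycles (7.1), and last ibrutinib on day 56. Day 56 ends cycle 2 (2 × 28), so both permissive sections apply. Dosing is assumed to be on schedule, on days 1, 15, 29 and so on.

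Doses given through day d = floor((d − 1)/14) + 1.

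The 4-week hold covers days 57 to 84, so item 9 applies from day 85. Doses through day 84: floor(83/14) + 1 = 6, the last on day 71. Two of the six (days 57 and 71) are nivolumab alone.

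For the lower end I use the nivolumab-alone results in Section 1.1.1: "Median PFS was 2.7, 4.0, and 4.2 months, respectively" for 0.3, 2 and 10 mg/kg, with a month taken as 30.44 days. Six months is taken as 26 weeks.

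| Nivolumab would otherwise run to | Doses under the option | Under item 9 | Forgone |
|---|---|---|---|
| Day 82 (2.7 months) | 6 | 6 | 0 |
| Day 122 (4.0 months) | 9 | 6 | 3 |
| Day 128 (4.2 months) | 10 | 6 | 4 |
| Day 182 (progression-free at 6 months) | 13 | 6 | 7 |
| Day 364 (no progression for a year) | 26 | 6 | 20 |

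The first row carries little weight. The 2.7-month median belongs to the 0.3 mg/kg arm, and 240 mg would equal 0.3 mg/kg only at 240/0.3 = 800 kg. The day-182 row describes the status that the design assumes for 70% of patients. Item 3 sets no 4-week allowance, so item 9, used here, is the more lenient of the two rules.

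**The case against.** The best defence is that *held* means a temporary pause. The protocol does separate withholding from discontinuing elsewhere: Table 1 withholds ibrutinib for the first three occurrences and discontinues it at the fourth, and Section 5.3.4 and the nivolumab tables make a similar distinction. Item 9 would then govern unresolved pauses, and 3.2.1 and 8.2 a decision to go on with nivolumab alone. This reading does preserve the option for a patient who chooses to stop ibrutinib outright. It fails for toxicity, because item 3 ends study treatment when an adverse event rules out further ibrutinib. It also has an odd result: a 5-week pause ends nivolumab while a permanent stop does not.

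A reader might infer more than the documents support, in four ways.

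- *That the option is abolished.* About 4 weeks of nivolumab alone survive item 9.
- *That scans are lost before 6 months.* Appendix 1 heads the follow-up column as 3-monthly, and Section 8.3 says "Once a subject has completed the End-of-Treatment Visit they will enter the Follow-up Phase". But footnote b attaches being "contacted approximately every 3 months" to treatment failure, relapse or new anticancer therapy, which a progression-free patient need not have had. The note "Disease assessment to be performed every 8 weeks" sits on the disease-assessment row, whose imaging lines are marked under follow-up, and suspected progression can be scanned at any time. Only if follow-up is read as 3-monthly would the scheduled scans by day 182 fall from 3 (days 57, 113, 169). They would fall to 1 if the interval runs from the End-of-Treatment visit (71 + 30 + 91 = day 192), or to 2 if it runs from the last dose (71 + 91 = day 162). That ambiguity affects every early stopper and is not created by item 9.
- *That Section 6.2.4 shows long holds leading to this conflict.* It says "treatment with ibrutinib should be held and not be restarted until the subject is clinically stable and has no signs of bleeding", but it gives no duration and contemplates a restart. Starting anticoagulation is not in itself toxicity or patient preference.
- *That sites will stop nivolumab.* The documents do not say which section a site would follow.

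Finally, item 9 is explicit and may be what the sponsor wants, for instance to keep the trial about the doublet. That is possible, but it would make 3.2.1 and 8.2 the sections in error, and an amendment would still be needed.

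**Conclusion.** The conflict is real and unresolved in the text. Items 9 and 3 of Section 9.2 withdraw a treatment that Sections 3.2.1 and 8.2 allow, apart from about 4 weeks under item 9. For a patient whose last ibrutinib dose is on day 56, the loss is 7 of 13 doses by day 182 if progression-free, and at most 20 of 26 over a year. It is 3 or 4 doses if progression comes at the medians reported for 2 and 10 mg/kg. These counts assume on-schedule dosing, an investigator who would have chosen to continue nivolumab, and no other reason to stop it. How many patients would be affected cannot be estimated from the documents, so no effect on the 6-month PFS count can be claimed. The level, power, sample size and decision rule stand. The protocol should be corrected, but the conflict does not undermine the design.

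**What to change.** Make these changes in one amendment.

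- Reword item 9: *If ibrutinib is held for more than 4 weeks, ibrutinib is permanently discontinued; nivolumab may continue at the investigator's discretion as allowed in Sections 3.2.1 and 8.2, with disease assessments every 8 weeks.*
- Put the same exception in item 3, and in item 1 where the toxicity is from ibrutinib only. A cross-reference is not enough, because item 3 as written ends study treatment.
- Make the two-cycle condition match in 3.2.1 and 8.2. Whether to keep it is the sponsor's choice.
- Report how many patients in the 6-month PFS analysis had part of their treatment as nivolumab alone.

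If the sponsor intended item 9 as written, delete the single-agent option from 3.2.1 and 8.2 instead.

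The cost is a few sentences. Infusions and assessments for these patients are already provided for under 3.2.1 and 8.2. The downside of the permissive fix is that some patients in the PFS count will have had part of their treatment as nivolumab alone. Sections 3.2.1 and 8.2 already allow this, and the added reporting makes it visible.
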